11.4 Electrocardiogram

Not applicable.

11.5 Other Safety Variables

Not applicable.

12. CLINICAL PHARMACOKINETIC AND PHARMACODYNAMIC ANALYSES

12.1 Pharmacokinetics Population and Pharmacodynamics Population

The Pharmacokinetic Set will consist of all subjects in the Safety Analysis Set with no major deviations related to investigational product intake, for whom the primary pharmacokinetic data are considered sufficient and interpretable, will be included in the Pharmacodynamic Set. Subjects with missing data in some, but not all the periods, will be included in the analysis set.

12.2 Pharmacokinetic Methods

All summaries and analyses of the pharmacokinetic data will be based on the Pharmacokinetic Set.

12.2.1 Concentration Data

The concentrations of C1 INH antigen in human plasma samples will be determined using an automated nephelometric assay on the Behring Nephelometer 2. The C1 INH activity in human plasma samples will be determined by a chromogenic assay using a commercially available kit.

12.2.2 Handling BLQ Values

The following procedures will be used for plasma concentrations below the lower limit of quantification (LLOQ) (reported as not quantifiable (NQ)):

Plasma samples that are BLQ are reported as zero on the data listings.

Samples that are BLQ are treated as zero in the calculation of summary statistics for the plasma concentrations at individual time points

Mean concentrations are reported as zero if all values are BLQ, and no descriptive statistics are reported. If the calculated mean (\pm SD) concentration is less than the LLOQ, the value will be reported as calculated.

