1.0 INTRODUCTION

Hereditary angioedema (HAE) is an autosomal dominant disease resulting from mutations of the C1 inhibitor (C1 INH) gene and deficient plasma C1 INH protein. Nearly all affected individuals experience symptoms of the disease; however, the symptoms vary in both their frequency and severity (Gompels et al., 2005; Zuraw, 2003). The diagnosis of a C1 INH deficiency is suggested by a history that includes recurrent attacks of angioedema, characterized by non-itching swelling of the skin or mucosa. Serum C4, C1 INH antigen, and functional C1 INH levels can be measured to assist with the diagnosis of HAE. A low level of C4 in combination with a low level of either C1 INH antigen (Type I HAE) or functional C1 INH (Type II HAE) are confirmatory for the diagnosis of HAE (Frank et al., 1976). In rare instances, C4 levels may be normal in HAE patients between attacks, but are almost always decreased during episodes of HAE swelling (Frank et al., 1976). In this circumstance, a low serum C4 level during an episode of idiopathic swelling can be used to confirm the diagnosis of HAE (Frank et al., 1976; Waytes et al., 1996).

Attacks of HAE are usually self-limiting, but can be quite painful, disfiguring, disabling, and sometimes fatal. Edema can involve the skin and visceral organs, but most frequently manifests in the extremities or bowel; the swelling generally lasts 2 to 5 days (Nzeako et al., 2001; Zuraw, 2008). Abdominal attacks have been reported to occur in >93% of patients and account for nearly 50% of all angioedema attacks (Zuraw, 2008). Not infrequently, an abdominal HAE attack can imitate a surgical emergency. Life-threatening laryngeal edema may also occur and this accounts for the majority of the 30% to 40% mortality rate reported for this disease (Agostoni and Cicardi, 1992; Bork et al., 2000).

Intravenous administration of C1 INH, the plasma protein that is deficient in patients with HAE, has been used in Europe for more than 30 years for the treatment of acute attacks of HAE (Wall and Frank, 1990; Gadek et al., 1980). C1 INH concentrates are prepared from pooled human plasma. The efficacy of purified C1 INH concentrates in the treatment of acute angioedema in HAE has previously been described (Agostoni et al., 1980; Bergamaschini et al., 1983; Logan and Greaves, 1984; Späth et al., 1984).

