1.1 CINRYZE® (C1 esterase inhibitor [human])

CINRYZE® (C1 esterase inhibitor [human]) consists of a protein fraction prepared from human plasma. The manufacturing process includes 3 virus inactivation/removal steps: polyethylene glycol precipitation, pasteurization, and nanofiltration. CINRYZE is a normal human plasma protein that is not subject to Cytochrome P450 metabolism, excretion, or pharmacokinetic (PK) drug-drug interactions exhibited by low molecular weight compounds.

CINRYZE was approved by the United States (US) Food and Drug Administration (FDA) for routine prophylaxis against angioedema attacks in adolescent and adult patients with HAE in October 2008. CINRYZE was approved throughout the European Union (EU), via the Centralized Procedure, in June 2011 for treatment and pre-procedure prevention of angioedema attacks in adults and adolescents with HAE, and routine prevention of angioedema attacks in adults and adolescents with severe and recurrent attacks of HAE who are intolerant to or insufficiently protected by oral prevention treatments, or patients who are inadequately managed with repeated acute treatment. CINRYZE has also received marketing authorization in Australia (2012), Canada (2012), India (2013), Switzerland (2013), and Israel (2013).

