In a post-approval open-label study (0624-400) there were no systemic thrombotic events in subjects (n=20) who received IV CINRYZE up to 2500 U every 3 or 4 days for up to 12 months. One subject developed a blood clot in an intravenous central catheter, which was treated locally without systemic complication. Nevertheless, patients with known risk factors for thrombotic events (including indwelling catheters) should be monitored closely.

Evaluation of the clinical PK and pharmacodynamics (PD) following IV administration of CINRYZE in subjects with HAE was primarily based on the results of Protocol LEVP 2006-5. After IV administration of CINRYZE 1000 U, functional C1 INH

¹ Mean observed 12-week HAE attack rate: 6.1 for CINRYZE vs. 12.7 for placebo per CINRYZE US Package Insert (2012).

concentrations increased from a mean baseline value of 0.31 U/mL to a maximum concentration (C_{max}) of 0.68 U/mL. Two consecutive 1000 U doses administered 60 minutes apart produced a mean C_{max} of 0.85 U/mL. Median time to maximum concentration (t_{max}) was approximately 1 to 2 hours. The mean terminal elimination half-life ($t_{1/2}$) of functional C1 INH was approximately 60 hours using noncompartmental methods. Mean clearance (CL) values for functional C1 INH were 0.85 and 1.17 mL/min for the single and double doses, respectively. Mean C_{max} values for C1 INH antigen following IV administration of CINRYZE were 1.48 and 1.70 U/mL for the single and double doses, respectively. Median t_{max} was approximately 1.5 hours. The mean $t_{1/2}$ of antigenic C1 INH was approximately 45 to 47 hours and mean CL was 0.70 mL/min.

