4.1 Inclusion Criteria

To be eligible for this protocol, a subject must:

1. Be a child (male or female), ≥ 6 to <12 years of age at the time of screening.
2. Have a confirmed diagnosis of Type I or Type II HAE and have a functional C1 inhibitor (C1 INH) level less than 50% of normal.
3. Have a history of ≥ 1.0 angioedema attacks per month (average) that are moderate¹ or severe² or require acute treatment³ during the 3 consecutive months prior to screening.
4. Agree to adhere to the protocol-defined schedule of assessments and procedures.
5. Have a parent(s)/legal guardian who is informed of the nature of the study provide written informed consent for the child to participate in the study before any study-specific procedures are performed (with assent from the child when appropriate).

Additional Inclusion Criteria (Qualifying for Randomization)

6. Have experienced ≥ 1.0 angioedema attacks per month (average) that are moderate¹ or severe² or require acute treatment³ during the 12-week baseline observation period.

¹ Moderate: Angioedema attack sign/symptom(s) interferes with the subject's ability to attend school or participate in family life and social/recreational activities.

² Severe: Angioedema attack sign/symptom(s) significantly limits the subject's ability to attend school or participate in family life and social/recreational activities.

³ 'Treatment' refers specifically to standard of care therapies used to treat an angioedema attack (e.g., C1 INH, kallikrein inhibitor, bradykinin receptor antagonist). Products used for the treatment of attack symptoms (e.g., analgesics, anti-emetics) do not qualify for this study inclusion criterion.

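### SAP 12.2.2 counts BLQ C1 INH results as zero although C1 INH is endogenous; if any occur, pre-dose means come out too low and pre- to post-dose changes too high

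*SAP*

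**What the plan says.** SAP 12.2.2 gives one rule for C1 INH plasma concentrations below the limit of quantification. For listings: "Plasma samples that are BLQ are reported as zero on the data listings". For tables: "Samples that are BLQ are treated as zero in the calculation of summary statistics for the plasma concentrations at individual time points". When nothing in a cell is quantifiable: "Mean concentrations are reported as zero if all values are BLQ, and no descriptive statistics are reported". There is no exception for pre-dose or trough samples.

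Protocol 1.1 describes the product in these words: "CINRYZE is a normal human plasma protein". Protocol 1.0 attributes HAE to "deficient plasma C1 INH protein", which is a shortage and not an absence. For functional activity after 1000 U, Protocol 1.1.2 reports that "concentrations increased from a mean baseline value of 0.31 U/mL to a maximum concentration" of 0.68 U/mL. Eligibility (Protocol 4.1) requires a "functional C1 inhibitor (C1 INH) level less than 50% of normal", with no lower bound.

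The change from pre- to post-dose in C1 INH functional activity, C1 INH antigen and C4 is a secondary efficacy variable (Protocol 7.3, SAP 10.3). SAP 10.3 states no separate BLQ rule for it. SAP 12.3 summarises concentrations at each nominal time by n, mean, SD, median, maximum and minimum. SAP 12.2.1 names the assays, but neither document gives an LLOQ.

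**The concern.** A BLQ result means that the true value lies somewhere below the LLOQ. For a foreign drug before the first dose, zero is a fair reading. For an endogenous protein that averages 0.31 U/mL in this disease it is not. It is less so once dosing has started: with a half-life of about 60 hours and doses every 3 or 4 days, part of each dose is still present at the next one.

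Any zero therefore pulls the mean below its true value and forces the minimum to zero. Because the pre-dose value is subtracted, the same zero makes the change too large. The cells are small: with 12 values, one true result of 0.15 U/mL set to zero lowers the mean by 0.15/12 = 0.0125 U/mL. In a listing, a censored result would look like a measured zero.

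At stake are the descriptive PK tables and listings and one secondary variable.

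**Working it through.** The plan gives no figure on this point to reproduce, so the check asks how large the bias could be.

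**Inputs from the documents.** Functional baseline mean 0.31 U/mL and peak 0.68 U/mL after 1000 U, so a rise of 0.37; half-life about 60 h (Protocol 1.1.2, from another study, LEVP 2006-5). Doses every 3 or 4 days, taken as 84 h; no washout (Protocol 3.0).

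**Assumptions.** LLOQ 0.10 to 0.30 U/mL; lognormal baseline with CV 50%; rise after 500 U half of that after 1000 U (0.185), with CV 30% on the rise.

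**Step 1: pre-dose mean at Visit 1a.** σ² = ln(1 + 0.5²) = 0.2231, so σ = 0.4724, and μ = ln 0.31 − σ²/2 = −1.2828. For LLOQ = L, let z = (ln L − μ)/σ. Then:

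- share BLQ = Φ(z)
- bias with zero = −0.31 × Φ(z − σ)
- bias with LLOQ/2 = that value + (L/2) × Φ(z)

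Example, L = 0.20: z = (−1.6094 + 1.2828)/0.4724 = −0.691. The share BLQ is 0.245. The bias with zero is −0.31 × Φ(−1.164) = −0.31 × 0.122 = −0.038. With LLOQ/2 it is −0.0379 + 0.10 × 0.245 = −0.013.

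| LLOQ (U/mL) | Share BLQ | Bias, zero | Bias, LLOQ/2 |
|---|---|---|---|
| 0.10 | 1.5% | −0.001 | −0.001 |
| 0.15 | about 10% | −0.012 | −0.005 |
| 0.20 | about 24% | −0.038 | −0.013 |
| 0.25 | about 41% | −0.076 | −0.024 |

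With CV 30% and LLOQ 0.20, about 9% are BLQ and the bias with zero is −0.016.

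**Step 2: change after the first dose.** Post-dose values are almost never BLQ, so the mean change rises by what the pre-dose mean loses. At LLOQ 0.20 and 1000 U it goes from 0.370 to 0.408 (0.038/0.370 = 10%). Against the assumed 500 U rise, the error is 0.038/0.185 = 21%.

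**Step 3: dose contrasts at steady state.** The fraction left after 84 h is 2^(−84/60) = 0.379. Accumulation is 1/(1 − 0.379) = 1.610. The trough increment on 1000 U is 0.37 × 0.379 × 1.610 = 0.226, and on 500 U it is 0.113. Mean troughs are then about 0.536 and 0.423 U/mL. The true contrasts (1000 U minus 500 U) are 0.113 for the trough and 0.370 − 0.185 = 0.185 for the change. Simulation with BLQ set to zero gives:

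| Baseline mean | LLOQ | BLQ troughs, 500 U / 1000 U | Trough contrast | Change contrast |
|---|---|---|---|---|
| 0.31 | 0.15 | 0.1% / 0% | 0.113 | 0.185 |
| 0.31 | 0.20 | 2% / 0% | 0.116 | 0.182 |
| 0.31 | 0.25 | 8% / 0.5% | 0.130 | 0.168 |
| 0.31 | 0.30 | 21% / 3% | 0.158 | 0.142 |
| 0.15 | 0.20 | 22% / 1% | 0.149 | 0.149 |

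The two contrasts move in opposite directions because the 500 U troughs are zeroed more often. That lowers the 500 U trough mean, and since the trough is subtracted, it raises the 500 U change.

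**The case against.** The strongest objection is that there may be no BLQ results at all. The LLOQ is unknown, and at 0.10 U/mL or below the effect is negligible for a baseline of 0.31. That baseline comes from another study and not from this age group, and the CV is assumed. Subjects may also stop commercial C1 INH prophylaxis as late as 3 days before dosing (Protocol 6.3.3), so some Visit 1a samples will contain residual product. All of this stands and makes the point conditional. It does not make zero a sound rule when a BLQ result does occur.

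The plan also limits the harm. The median is already reported and does not move while fewer than half the values are BLQ. C1 INH levels are only described: the testing method of SAP 10.1 is extended to the two severity scores and the count of acutely treated attacks, not to these changes. That stands too, but the mean and the change remain wrong.

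A reader might infer three stronger things that the documents do not support:

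- **That the rule inflates the dose contrast.** This is true of trough levels only. For the listed variable, the steady-state change, the contrast narrows. At Visit 1a randomization balances BLQ results on average. At Visit 1b the pre-dose sample is a trough on the other dose, so the direction depends on sequence.
- **That zeros enter the population PK model.** SAP 12.2.2 covers listings and summaries by time point, and notes that such results are reported as not quantifiable. SAP 12.2.3 reports modelling separately and does not say that it takes zeros.
- **That C4 is affected.** C4 falls under SAP 12.4, which states no BLQ rule, and nothing suggests that C4 results will be BLQ.

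**Conclusion.** The point holds in a conditional form and is minor. The zero rule is wrong in principle for an endogenous protein. Whenever a sample is BLQ, it biases the mean at that time point low and the pre- to post-dose change high. Visit 1a pre-dose is the main exposure, since it precedes any study drug.

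For functional activity, with a mean of 0.31 U/mL and an assumed lognormal CV of 50%, the pre-dose bias runs from about 0.001 U/mL at LLOQ 0.10 to 0.076 at LLOQ 0.25. Dose contrasts shift by about 0.003 U/mL at LLOQ 0.20. They shift by about 0.017 at 0.25 and 0.04 to 0.05 at 0.30, upward for troughs and downward for changes. Lower baselines in these children would bring such shifts in at a lower LLOQ. No size is given here for antigen, because the documents do not support an estimate. The attack-based primary endpoint is untouched.

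**What to change.** Amend SAP 12.2.2 as follows:

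- List BLQ results as '<LLOQ' and not as 0.
- For C1 INH antigen and functional activity, use LLOQ/2 in place of zero in means and in pre- to post-dose changes.
- State the LLOQ of each assay, and show the number of BLQ samples per dose and time point beside the median already planned.

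The cost is one paragraph and one programming rule; if no sample is BLQ, no result changes. The downside is that means depend slightly on the substituted value and some bias remains. In the table above, LLOQ/2 takes the bias from 0.038 to 0.013 at LLOQ 0.20 and from 0.076 to 0.024 at 0.25, so roughly a third is left. The BLQ counts let a reader see where that matters.

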12.2.3 Pharmacokinetic Parameters

The pharmacokinetic parameters using non-compartmental analysis (NCA) will be estimated for subjects who provided optional PK samples and will be reported separately. Population modeling and simulation will be conducted using sparse PK concentrations from all subjects and will be reported separately.

12.3 Statistical Analysis of Pharmacokinetic Data

Plasma concentrations at each nominal sampling time will be summarized using descriptive statistics (number of observations, mean, standard deviation, median, maximum and minimum).

12.4 Pharmacodynamic Methods

All summaries and analyses of the pharmacodynamic data will be based on the Pharmacodynamic Set.

12.4.1 Concentration data

The concentrations of C4 complement in human plasma samples will be determined using an automated nephelometric assay on the Behring Nephelometer 2.

12.4.2 Pharmacodynamic Parameters

Pharmacodynamic parameters will be determined from the plasma concentration-time data for C4. All calculations will be based on actual sampling times. The analysis will be reported separately.

12.5 Statistical Analysis of Pharmacodynamic Data

Plasma concentrations of C4 at each nominal sampling time will be summarized using descriptive statistics (number of observations, mean, standard deviation, median, maximum, minimum).

12.6 Analyses of Pharmacokinetic/Pharmacodynamic Relationships

Not applicable.

12.7 Changes in the Pharmacokinetic, Pharmacodynamic, PK/PD or Statistical Methods from Those stated in the Protocol

There will not be a formal PK/PD analysis as stated in the protocol since this was not listed as part of the objectives in the protocol. This analysis will be done outside of the CSR for this study.

12.8 Pharmacokinetic References

Not applicable.

12.9 Pharmacokinetic and Pharmacodynamic Tables and Listings

Formats and numbering of the tables and listings will be finalized prior to the completion of the Clinical Study Report. No revision to this document is required for changes which do not affect the statistical or pharmacokinetic methods, definitions, or rules defined in this document.

In the event that a limited number of samples yield measurable concentrations, the pharmacokinetic tables and listings will be generated as deemed appropriate. No revision of this document will be required.

Detailed information will be presented in Section [20](#).

13. OTHER ANALYSES

13.1 Quality of Life Analyses

EQ-5D-Y1 (Youth version of EQ-5D) is a descriptive system of youth health-related quality of life states consisting of five dimensions, each of which can have one of three responses. The responses record the level of severity within a particular EQ-5D dimension. EQ-5D-Y is not intended for use in children 6 years of age (Noyes and Edwards, 2011); however in this study all subjects (6 to 11 years of age and where translated language version is available) will be assessed. The EQ-5D-Y will be completed by the subject at the time points specified in Schedules 1-4, as well as on each day that a subject experiences signs or symptoms of an angioedema attack.

Results of the EQ-5D-Y health status questionnaire will be presented in accordance with the EQ-5D-3L User Guide (version 4.02), and adapted as appropriate for the youth version. EQ-5D-Y will be summarized by the number of subjects and the percentage of subjects in each category at each timepoint. Descriptive statistics for VAS Score and changes from baseline at each post-dose visit and final visit will be presented by treatment. The baseline for VAS Score is defined as the average of all pre-dose visits in Baseline Observation Period.

13.2 Health Economics and Outcomes Research Analyses

Not applicable.

¹ EQ-5D[™] is a trade mark of the EuroQol Group.
2. EQ-5D-3L User Guide: Basic information on how to use the EQ-5D-3L questionnaire. Version 4.0, April 2011. Published by the EuroQol Group Executive Office on behalf of the EuroQol Group.

14. INTERIM ANALYSIS

Not applicable, as no interim analysis is planned for this study. However, there will be an administrative look at N = 6 subjects for EU regulatory purposes which is described in the protocol amendment version 4.0 (26. Jan. 2015). Requested TFL will be described in Section [20](#).

15. DATA MONITORING/REVIEW COMMITTEE

Not applicable, as no data monitoring review is planned for this study.

16. COMPUTER METHODS

Statistical analyses will be performed using Version 9.1.3 (or newer) of SAS[®] on a suitably qualified environment.

17. CHANGES TO ANALYSES SPECIFIED IN PROTOCOL

Analysis populations to analyses specified in the protocol are modified in using Shire standard definition and wording for SAP. Details are presented in Section 4.1, Section 4.2, Section 4.3, Section 4.4, and Section 4.5.

18. DATA HANDLING CONVENTIONS

18.1 General Data Reporting Conventions

Continuous variables will be summarized using the following descriptive statistics: n, mean, median, standard deviation, minimum, and maximum. Categorical and count variables will be summarized by the number of subjects (n) and the percent of subjects in each category.

Unless specified otherwise, median, min/max will be presented to the same decimal places as the raw data. Percentage, mean will be presented to 1 more decimal places than the raw data. Standard deviation and standard error will be presented to 2 more decimal places than the raw data.

p-values will generally be presented to 4 decimal places; values less than 0.0001 will be presented as <0.0001.

Treatment Columns Displayed in Summary Tables

The treatment columns displayed will differ between summary tables. Tables that summarize information solely from the pre-therapy or post-therapy periods will generally have the following three treatment columns displayed:

Sequence A/B

Sequence B/A

Total

Tables that summarize efficacy information solely from the on-therapy period will generally have the following six treatment columns displayed:

A/B: Period 1 Cinryze 500 U

A/B: Period 2 Cinryze 1000 U

B/A: Period 1 Cinryze 1000 U

B/A: Period 2 Cinryze 500 U

Treatment A: Cinryze 500 U

Treatment B: Cinryze 1000 U

Tables that summarize information across on-therapy visits will generally have the following 3 treatment columns displayed:

Treatment A: Cinryze 500 U

Treatment B: Cinryze 1000 U

Total (if needed)

Tables that summarize information across visits, including pre-therapy (observation period) and on-therapy visits, will generally have the following 8 treatment columns displayed:

Observation Period (prior to A/B)

A/B: Period 1 Cinryze 500 U

A/B: Period 2 Cinryze 1000 U

Observation Period (prior to B/A)

B/A: Period 1 Cinryze 1000 U

B/A: Period 2 Cinryze 500 U

Treatment A: Cinryze 500 U

Treatment B: Cinryze 1000 U

The "Observation Period (prior to A/B)" and "Observation Period (prior to B/A)" columns will be the only columns populated for the pre-therapy visit (observation period) in such tables.

18.2 Derived Efficacy Variables

Not applicable.

18.3 Repeated or Unscheduled Assessments of Safety Parameters

If a subject has repeated assessments before the date and time of dose of investigational product, then the results from the final assessment made prior to the date and time of dose of investigational product will be used as baseline. If clinical discharge assessments are repeated or unscheduled, the latest assessment will be used as the clinical discharge assessment for generating descriptive statistics. However, all post-baseline assessments will be used for post-baseline overall PCI value determination, and all assessments will be presented in the data listings.

In the following sections, where missing times are seen on the database, they are handled using the same underlying assumptions as for missing dates.

